3.4.1. Dose limiting toxicity

Number and percentage of patients with at least one DLT before the end of the first cycle, type of DLT and listing of PTs, verbatim and worst grade of AE declared as DLT will be provided in the DLTES.

Listing of patients with at least one DLT, type of DLT and PTs, verbatim will also be provided in the DLTES.

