3.4. Endpoints

Table (3.4) 1 - Endpoints for dose escalation phase I part – Arm A

	Objectives	Endpoints
Primary	To determine the safety profile and tolerability of S64315 in combination with azacitidine in patients with AML	
 - Incidence of DLTs starting from the LID period to the end of the first cycle of treatment of S64315 in combination with azacitidine - Incidence and severity of AEs and SAEs according to NCI CTCAE v5.0 - Recording of any change or addition of a new concomitant treatment - Laboratory tests: haematology with differential, blood biochemistry, thyroid function, blood coagulation, urinary analysis, hepatitis markers, TLS monitoring, cardiac markers follow up - Complete physical examination, ECOG performance status, vital signs measurements - ECG parameters, cardiac function assessment - Left ventricular ejection fraction (LVEF) - Dose interruptions, reductions and dose intensity
Secondary	
To determine the PK profile of S64315 and azacitidine administered in combination, and potential metabolites
 
To evaluate the anti-leukemic activity of S64315 in combination with azacitidine
	
PK parameters of S64315 and azacitidine administered in combination, and potential metabolites if applicable, in plasma (e.g. C_{inf}, t_{inf}, AUC_{last}, t_{last}, C_{last}, AUC, $t_{1/2,z}$, CL and Vd)
 
 - CR rate, ORR (including CR/CRi/MLFS), Best Overall Response (BOR), Duration of Response (DOR), Progression Free Survival (PFS), Overall survival (OS) - Anti-leukemic activity assessment using blood, BMA and BMB if available according to ELN 2017 response criteria (Döhner, 2017)

	Objectives	Endpoints

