10.4.1. Evaluation criteria

10.4.1.1. Safety criteria

10.4.1.1.1. Dose escalation phase I part

- Incidence of DLT during the LID period and Cycle 1
- Incidence and severity of AEs and SAEs
- Change or addition of a new concomitant treatment
- Laboratory tests: haematology with differential, blood biochemistry, thyroid function, blood coagulation, urinary analysis, hepatitis markers, TLS monitoring, cardiac markers
- Complete physical examination, ECOG PS
- Vital signs
- ECG and cardiac function parameters
- LVEF
- Pregnancy test for WOCBP
- Dose interruptions, reductions and dose intensity

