10.4.3.1. Dose escalation phase I part

- Included Set 1 (IS1) corresponds to all included patients during the dose escalation phase I part
- Safety Set 1 (SS1) corresponds to patients who received at least one dose of IMP during dose escalation phase I part. It will be used for all safety and efficacy analyses
- Dose-Limiting Toxicity Evaluable Set (DLTES) corresponds to patients from the SS 1 who are evaluable for DLT according to the criteria defined in [section 4.1.3.6](#)

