10.4.4.2. Safety

The safety analyses will be performed on the SS sets, SS1 and SS2, by dose level and overall.

DLT until the end of Cycle 1

Number and percentage of patients in the DLTES with DLT occurrence from the LID period to the end of the first cycle will be tabulated by dose level and overall.

DLT after the end of Cycle 1

Number and percentage of patients evaluable for DLTs, with occurrence of DLT after the end of the first cycle will be tabulated by dose combination and overall.

Emergent adverse event

NCI CTCAE v5.0 will be used to classify all adverse events.

Number of Emergent adverse event (EAE), number and percentage of patients reporting at least one EAE will be summarised by System Organ Class and Preferred Term, overall and by dose level. The same analysis will be performed for serious EAEs and SAEs.

Some analyses will be performed by worst on-treatment grade, severity, relationship to the IMP, outcome and action taken.

Clinical laboratory evaluation

Laboratory parameters will be graded according to NCI CTCAE v5.0. For laboratory tests where grades are not defined by NCI CTCAE v5.0, results will be classified according to the laboratory reference ranges.

The following summaries will be generated separately for each haematology and biochemistry tests:

- for laboratory tests where grades are defined by NCI CTCAE v5.0, shift tables comparing the worst on-treatment grade to the grade at baseline
- for laboratory tests where grades are not defined by NCI CTCAE v5.0, shift tables comparing the classification according to the laboratory normal ranges to baseline

Urinalysis abnormalities will be described using shift tables comparing the worst on-treatment value (Positive, Trace, Negative) to the value at baseline.

Physical examination including vital signs, body weight and ECOG PS

These criteria will be described using baseline value, worst on-treatment value and change from baseline to worst on-treatment value.

ECG parameters and LVEF

Quantitative parameters (QT interval corrected and LVEF) and qualitative parameters (ECG abnormalities) will be described.

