1.2. Study endpoints

The endpoints for the primary objective are:

- The incidence of DLT(s) starting from the lead-in dose (LID) period to the end of each cycle of treatment of S64315 in combination with azacitidine.
- The incidence and severity of adverse events (AEs) and serious adverse events (SAEs) according to the National Cancer Institute Common Terminology Criteria for Adverse Events (NCI-CTCAE) version 5.0.
- The recording of any change or addition of a new concomitant treatment.
- The laboratory tests: haematology with differential, blood biochemistry, thyroid function, blood coagulation, urinary analysis, hepatitis markers, Tumour Lysis Syndrome (TLS) monitoring, cardiac markers follow up.
- The complete physical examination, Eastern Cooperative Oncology Group (ECOG) performance status and vital signs measurements.
- The electrocardiogram (ECG) parameters and cardiac function assessment.
- The left ventricular ejection fraction (LVEF).
- The dose interruptions, reductions and dose intensity.

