3. STATISTICAL METHODS

3.1. General considerations

Descriptive statistics depending on the nature of the criteria and the number of patients by dose level combinations:

- For **qualitative data**, number of observed values, number and percentage of patients per class will be presented. Unless otherwise specified in the TLG, no class "Missing" is considered.
- For **quantitative data**, number of observed values, mean, standard deviation (SD), minimum (min) and maximum (max), median, first (Q1) and third (Q3) quartiles.

For **Event**:

- Number of patients (or cycles) having experienced the event (n).
- Number of events that occurred (for AE analyses only) (NAE).
- Number of patients (or cycles) at risk for the event (N).
- Global incidence rate (%),
 - o calculated as the ratio between the number of patients (or cycles) having experienced the event (n) and the number of patients (or cycles) at risk at the beginning of the study (N).

Globally, mean, standard deviation and the percentage will be submitted only to the dose level combinations with sufficient number of patients.

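### SAP 3.4.1 leaves out, without a stated reason, the protocol's table of DLTs after cycle 1, although SAP 1.2 runs the DLT endpoint through every cycle

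*SAP*

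**What the plan says.** Protocol 10.4.4.2 opens with its scope: "The safety analyses will be performed on the SS sets, SS1 and SS2, by dose level and overall". SS1 is the escalation safety set (protocol 10.4.3.1). Under separate subheadings the section then plans a cycle 1 DLT table in the DLTES and a second table, split by dose combination with an overall total: "Number and percentage of patients evaluable for DLTs, with occurrence of DLT after the end of the first cycle will be tabulated". Protocol 4.1.3.5 keeps DLT monitoring open after cycle 1 in case toxicity is delayed or builds up, and protocol 8.1 says that monitoring continues at all cycles.

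The escalation DLT endpoint itself stops at cycle 1. Table (3.4) 1 reads "Incidence of DLTs starting from the LID period to the end of the first cycle of treatment", and protocol 10.4.1.1.1 reads "Incidence of DLT during the LID period and Cycle 1".

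SAP 1.2 words the same endpoint differently: "The incidence of DLT(s) starting from the lead-in dose (LID) period to the end of each cycle of treatment". SAP 3.4.1 then plans one DLT summary, in the DLTES: "Number and percentage of patients with at least one DLT before the end of the first cycle, type of DLT", with preferred terms, verbatim and worst grade. It adds a listing of DLTES patients with at least one DLT, with no time limit stated. SAP 4.2.3.1 defines a DLT and says that DLT status is taken from the investigator's entry and is not derived again.

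**The concern.** The protocol planned a count and percentage of late DLTs and the SAP text does not. The SAP explains other omissions. Efficacy and patient follow-up observations are dropped for the abbreviated report (SAP 1, 3.2.6, 3.3), and Arm B and the expansion part will not be conducted (SAP 1.3). None of these reasons reaches late DLTs in escalation patients, and SAP 1 keeps the safety profile in scope.

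The SAP also disagrees with itself: its endpoint runs to the end of each cycle, but its only DLT table stops at cycle 1. At stake is complete reporting of a planned safety output under the primary safety objective. A labelled late-DLT proportion cannot be rebuilt from the adverse event tables, because those tables do not identify which events the investigator declared as DLTs.

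**Working it through.** The omission is a matter of text, so the first four steps compare passages. The fifth uses assumed counts to show why the denominator must be stated.

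1. **Does the late table apply to escalation?** Yes. The scope sentence of protocol 10.4.4.2 names SS1, so cancelling the expansion part removes the SS2 half only.

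2. **Is it anywhere in the SAP?** SAP 3.4.1 has the cycle 1 table and the listing. SAP 4.2.3.1 has only the definition. No other section summarises DLTs after cycle 1.

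3. **Which endpoint wording differs?** Protocol Table (3.4) 1 and 10.4.1.1.1 agree on the lead-in period plus cycle 1, and the SAP 3.4.1 table matches them. SAP 1.2 is the text that differs. Protocol Table (3.4) 2 has no time limit, but it belongs to the expansion part.

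4. **What is the denominator?** Protocol 10.4.4.2 names the DLTES for cycle 1 but uses a different phrase, patients evaluable for DLTs, for the later table. Three candidates exist:
   - The DLTES, which protocol 10.4.3.1 defines as "patients from the SS 1 who are evaluable for DLT". Evaluability is judged on cycle 1, and SAP 2.1 keeps patients whose treatment was stopped for a cycle 1 DLT.
   - The general rule in SAP 3.1, which divides by patients at risk at the start of the study. This too counts patients never treated after cycle 1.
   - The rule in protocol 4.1.4 and 10.3.2 for DLTs after cycle 1: three or more S64315 doses from cycle 2, unless a DLT limited dosing. It was written for expansion monitoring, but it brings in evaluable escalation patients treated at the RP2D. It is the only post-cycle-1 evaluability rule in the documents.

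5. **How much can the choice matter?** The documents give no late-DLT counts. Assume a dose level with 6 DLTES patients and one late DLT:
   - all 6 in the denominator: 1/6 = 17%;
   - 4 evaluable after cycle 1: 1/4 = 25%;
   - 3 evaluable: 1/3 = 33%;
   - 2 evaluable: 1/2 = 50%.

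   Any such figure is imprecise. Exact 95% intervals are 0 to 46% for 0/6 and 0.4 to 64% for 1/6. With 18 patients overall, the number of evaluable patients in protocol 10.2.8, 1/18 gives 0.1 to 27%.

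**The case against.** The strongest reply is that little is lost. The primary DLT endpoint is fully tabulated. Only lead-in and cycle 1 DLTs enter the BLRM (protocol 4.1.3.5). The pause rule for late DLTs belongs to the expansion part, which will not be conducted (SAP 1.3, 1.3.1). The SAP 3.4.1 listing has no time limit, so late DLTs in DLTES patients may appear there. Adverse events by grade, relationship and action taken (SAP 3.4.2), together with interruptions, delays, dose modifications and patients per cycle (SAP 3.2.5.1), show much of the late toxicity. The table shells are a separate document (SAP 1), not available here, and might contain the table.

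Most of this stands, and it limits the weight of the point. It does not close the gap. The listing specifies neither cycle of onset nor n/N. It also leaves out anyone outside the DLTES, such as a patient who missed the cycle 1 minimum exposure and later had a declared DLT. Imprecision is no reason to omit the table, since the cycle 1 table, which is kept, has the same limitation. The claim here concerns the SAP text, not the shells.

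A second reply is that the wording of SAP 1.2 is not a stray error, because the protocol does monitor DLTs at all cycles. That is fair, and it bears on the remedy: simply cutting SAP 1.2 back to cycle 1 would remove late DLTs from the SAP's endpoint list.

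**Conclusion.** The point holds as a gap between protocol and SAP: one of the protocol's two DLT tables is missing from the SAP text, with no reason given. It should be corrected, but it does not undermine the trial's main safety analysis.

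A reader might infer more than the documents support:
- *That the primary DLT endpoint goes unreported.* It does not; the SAP 3.4.1 table matches protocol 3.4 and 10.4.1.1.1.
- *That late DLTs would be invisible, or that a dose decision is compromised.* Several outputs show late toxicity, and no remaining dose decision uses the missing percentage.
- *That the late denominator is wholly undefined, or is plainly the DLTES.* Protocol 4.1.4 and 10.3.2 contain a rule, and protocol 10.4.4.2 words the two denominators differently. Whether the expansion rule governs this table is open, because 10.4.4.2 does not cite it.

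The size of the effect on any reported rate cannot be determined. The 17 to 50% range rests on assumed counts and shows only how sensitive the percentage is to the denominator. It does not measure the omission.

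**What to change.** In SAP 3.4.1, keep the cycle 1 table in the DLTES as the primary DLT analysis. Add the protocol's table of DLTs after cycle 1 as n/N (%), by dose level and overall.

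State the denominator of the added table. Either adopt the evaluability rule of protocol 4.1.4 and 10.3.2 or justify another set. Do not use all patients at risk at the start of the study (SAP 3.1).

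In SAP 1.2, word the primary DLT endpoint to the end of cycle 1, as protocol 3.4 does, and name DLTs after cycle 1 as a separate safety output. If the table is being dropped on purpose, one sentence saying so, with the reason, should replace the silence.

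The cost is one descriptive table and one wording change. DLT status is already on the DLT and adverse event eCRF pages (SAP 4.2.3.1), and patients per cycle are already tabulated (SAP 3.2.5.1). The drawback is imprecise percentages, which should be read with their numerators and denominators.

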3.4.2. Adverse events

Number of events, number and percentage of patients reporting at least one event, presented by primary SOC and PT (depending on the analysis), will be provided for SAEs over the study period and for treatment emergent adverse events (TEAEs).

TEAE will be described according to the seriousness, the worst grade, the severity, the relationship, the action taken regarding the IMP(s), the requirement of added therapy and the outcome.

Of note, the seriousness and the relationship with the IMPs (S64315 and/or azacitidine) of the adverse event are based on the investigator's opinion, but it includes also the sponsor decision to upgrade the seriousness and/or the relation to IMP(s) (the causal relationship will not be upgraded for EudraCT analyses).

The National Cancer Institute Common Terminology Criteria for Adverse Events Common Terminology Criteria for Adverse Events (NCI-CTCAE) classification version 5.0 will be used to classify all adverse events.

3.4.3. Death

Number and percentage of deaths will be described on each period (during the treatment and follow-up period / during the treatment period / during the follow-up period). Reason of death on each period will be provided in terms of qualitative data. During treatment period, reason will be presented by SOC and PT, whereas during the follow-up period it will be presented in terms of either progressive disease or other reason.

3.4.4. Clinical laboratory evaluation

Descriptive statistics on quantitative value and value by grade at baseline and worst grade on treatment according to the grade at baseline will be provided for gradable parameters (see [Table \(3.4.4\) 1](#)).

Table (3.4.4) 1 – Gradable parameters

Parameter		Worst Highest	Worst lowest	Gradable at baseline*
Blood biochemistry	Alanine aminotransferase (ALT)	High ALT	NA	No
	Albumin	NA	Low albumin	Yes
	Alkaline phosphatase (ALP)	High ALP	NA	No
	Amylase	High amylase	NA	Yes
	Aspartate aminotransferase (AST)	High AST	NA	No
	Bilirubin (total)	High total bilirubin	NA	No
	Cholesterol (total)	High cholesterol	NA	Yes
	Creatine phosphokinase (CPK)	High CPK	NA	Yes
	Gamma-glutamyl transferase (gamma-glutamyl transpeptidase) (GGT)	High GGT	NA	No
	Creatinine (serum)	High serum creatinine	NA	Yes
	Glucose	NA	Hypoglycemia	Yes
	Lypase	High lipase	NA	Yes
	Magnesium	Hypermagnesemia	Hypomagnesemia	Yes
	Potassium	Hyperkalemia	Hypokalemia	Yes
	Sodium	Hypernatremia	Hyponatremia	Yes
	Triglycerides	High triglycerides	NA	Yes
	Ionized calcium	High ionized calcium	Low ionized calcium	Yes
Blood haematology	Haemoglobin	High haemoglobin	Anemia	Yes for Low / No for High
	Lymphocytes	NA	Low lymphocytes	Yes
	Neutrophils	NA	Low neutrophils	Yes
	White blood cells (WBC)	NA	Low WBC	Yes

	Platelets	NA	Low platelets	Yes
Blood coagulation	Activated partial thromboplastin time (aPTT)	High aPTT	NA	Yes

Descriptive statistics on quantitative value and value by reference ranges at baseline and worst value on treatment according to baseline, with respect to the lower-limit normal (LLN) and the upper-limit normal (ULN) or by classes (<LLN / [LLN-ULN] / >ULN or normal / mild / moderate / severe for creatinine clearance) will be provided for non-gradable parameters (see [Table \(3.4.4\) 2](#)) and for parameters gradable post-baseline but non-gradable at baseline, in which case only baseline values will be presented.

Table (3.4.4) 2 – Non Gradable parameters

Parameter		Worst Highest	Worst lowest
Blood biochemistry	Bicarbonates	NA	Low bicarbonates
	Uric acid	High uric acid	NA
	Calcium (total)	Hypercalcemia	Hypocalcemia
	Creatinine clearance (approximated by the Modification of Diet in Renal Disease Glomerular Filtration Rate (MDRD GFR))	NA	Low creatinine clearance (Normal/mild/moderate/severe)
	Direct bilirubin	High direct bilirubin	NA
	High-density lipoprotein (HDL)	High HDL	NA
	Lactate dehydrogenase (LDH)	High LDH	NA
	Low-density lipoprotein (LDL)	High LDL	NA
	Phosphorus	NA	Hypophosphatemia
	Troponin I	High troponin I	NA
	Troponin T	High troponin T	NA
	Urea	High urea	NA
	Urea nitrogen (blood) (BUN)	High BUN	NA
Blood haematology	Basophils	NA	Low basophils
	Eosinophils	High eosinophils	NA
	Haematocrit	High haematocrit	Low haematocrit
	Monocytes	High monocytes	NA
	Red Blood Cell (RBC) Count	High RBC	Low RBC
	Lymphocytes	High lymphocytes	NA

	White Blood Cell (WBC) Count	High WBC	NA
Thyroid function	T3 free	High T3 free	Low T3 free
	T4 free	High T4 free	Low T4 free
	Thyroid Stimulating Hormone (TSH)	High TSH	Low TSH
Cardiac markers	Creatine PhosphoKinase Myocardial Band (CPK-MB) activity	High CPK-MB activity	NA
	CPK-MB mass	High CPK-MB mass	NA
	Brain Natriuretic Peptide (BNP)	High BNP	NA
Blood coagulation	International normalized ratio (INR)	High INR	NA

For urinalysis parameters haematuria, glycosuria, proteinuria, ketonuria: Descriptive statistics at baseline and worst value on treatment period, by classes (negative, trace, positive).

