5.3.2. Medical and therapeutic criteria

15. Adequate haematological function based on the last assessment performed within 7 days prior to the first IMP administration, defined as:
 - Circulating white blood cell count < 10 G/L (only use of hydroxycarbamide or leukapheresis before study drug initiation is allowed to achieve this inclusion criterion)
16. a. Adequate renal function based on the last assessment performed within 7 days prior to the first IMP administration defined as calculated creatinine clearance > 60 mL/min/1.73m², determined by MDRD ([Appendix 4](#))
17. Adequate hepatic function based on the last assessment performed within 7 days prior to the first IMP administration defined as:
 - AST and ALT < 1.5 x ULN and
 - Total serum bilirubin level < 1.5 x ULN, except for patients with known Gilbert's syndrome (confirmed by the UGT1A1 polymorphism analysis) who are excluded if total bilirubin > 3.0 x ULN or direct bilirubin > 1.5 x ULN

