^c ‘Combined’ defined as: total bilirubin increase to the defined threshold concurrently with ALT/AST increase to the defined threshold

^d ‘Cholestasis’ defined as: ALP elevation [$> 2 \times \text{ULN}$ and $R \text{ value} < 2$] in patients without bone metastasis, or elevation of ALP liver fraction in patients with bone metastasis

Note: (The R value is calculated by dividing the ALT by the ALP, using multiples of the ULN for both values. It denotes the relative pattern of ALT and/or ALP elevation is due to cholestatic or hepatocellular liver injury)

^e If combined elevations of AST or ALT and total bilirubin do not meet the defined thresholds, follow the instructions for isolated elevation of total bilirubin and isolated elevation of AST/ALT, and take a conservative action based on the degree of the elevations (e.g. discontinue treatment at the situation when omit dose is needed for one parameter and discontinue treatment is required for another parameter). After all elevations resolve to the defined thresholds that allow treatment re-initiation, restart the treatment either at the same dose or at one dose lower if a criterion for dose reduction is met.

^f LFT include albumin, ALT, AST, total bilirubin (fractionated if total bilirubin $> 2.0 \times \text{ULN}$), ALP (fractionated if ALP $> 2.0 \times \text{ULN}$) and GGT. For isolated elevations of any grade of ALP and/or GGT, maintain dose level.

^g Antidiarrheal medication is recommended at the first sign of abdominal cramping, loose stools or overt diarrhoea.

* Note: Patients enrolled with Gilbert’s syndrome and elevated baseline bilirubin between $> 1.5 \times \text{ULN}$ and $\leq 3.0 \times \text{ULN}$ or direct bilirubin $\leq 1.5 \times \text{ULN}$ can continue treatment.

**Table (8.12) 2 - Criteria for interruption and re-initiation of azacitidine
(see E.U. azacitidine SmPC)**

Dose adjustment due to haematological toxicity
 
Haematological toxicity is defined as the lowest count reached in a given cycle (nadir) if platelets $\leq 50.0 \times 10^9/L$ and/or absolute neutrophil count (ANC) $\leq 1 \times 10^9/L$. Recovery is defined as an increase of cell line(s) where haematological toxicity was observed of at least half of the difference of nadir and the baseline count plus the nadir count (i.e. blood count at recovery \geq nadir count + $(0.5 \times [\text{baseline count} - \text{nadir count}])$).
														

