4.2.3. Safety**4.2.3.1. Dose Limiting Toxicity (DLT)**

A DLT is defined as:

- A clinically significant adverse event graded according to the NCI-CTCAE version 5.0, observed following the administration of the test drugs.
- Assessed as unrelated to disease progression, intercurrent illness, or concomitant Medications.
- At least possibly related to the test drug(s) by the investigator and meeting any of the criteria included in [Table \(4.2.3.1\) 1](#).

DLT will be reported based on investigator, using the ‘Dose limiting toxicity (DLT)’ / ‘Adverse event’ e-CRF page, and not recalculated.

Table (4.2.3.1) 1 –Toxicity criteria

TOXICITY	DLT CRITERIA
Eye disorders: blurred vision; cataract; corneal ulcer; dry eye; eye pain	Grade ≥ 3 confirmed by an ophthalmologic examination
GI disorders	Grade ≥ 3 nausea, vomiting or diarrhoea resulting in hospitalization, tube-feeding or use of total parenteral nutrition (TPN) Grade 4 diarrhoea
Renal abnormalities	Grade ≥ 3 serum creatinine
Hepatic abnormalities	AST or ALT ≥ 3 xULN along with a total bilirubin > 2.0 xULN and confirmed Hy’s law cases according to FDA guidance; For patients with elevated baseline AST or ALT or total bilirubin: [AST or ALT > 2.0 xbaseline AND > 3.0 xULN] OR [AST or ALT > 8.0 xULN], whichever is lower, combined with [total bilirubin > 2.0 x baseline AND > 2.0 xULN] Isolated Grade 3 AST or ALT which does not resolve within 7 days to Grade ≤ 1 Isolated Grade 4 AST or ALT
For any Grade ≥ 3 hepatic toxicity which does not resolve within 7 days to Grade ≤ 1 level or baseline, an abdominal CT scan or hepatic echography must be performed.	
Pancreatic abnormalities	Grade ≥ 3 serum lipase and/or serum amylase Grade ≥ 3 pancreatitis
For any Grade 3 or Grade 4 pancreatic toxicity, which does not resolve within 7 days to Grade ≤ 1 level or baseline, an abdominal CT scan must be performed	
Creatine kinase (CK) / Creatine phosphokinase (CPK)	Grade ≥ 3 serum CK/CPK Grade 3 isolated electrolyte abnormalities (i.e. those occurring without clinical consequence) not recovered with or without intervention, to Grade < 2 level within 72 hours

Electrolyte abnormalities (including magnesium, calcium, phosphorus, etc.) clinically significant	Any Grade 4 electrolyte abnormality

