Total bilirubin increased (umol/L)	>ULN – 1.5 x ULN if baseline is normal [≤ULN]; 1.0 x baseline – 1.5 x baseline if baseline is abnormal [>ULN]	>1.5 x ULN – 3.0 x ULN if baseline is normal [≤ULN]; >1.5 x baseline – 3.0 x baseline if baseline is abnormal [>ULN]	>3.0 x ULN – 10.0 x ULN if baseline is normal [≤ULN]; >3.0 – 10.0 x baseline if baseline is abnormal [>ULN]	>10.0 x ULN if baseline is normal [≤ULN]; >10.0 x baseline if baseline is abnormal [>ULN]
CPK (IU/l) - high	>ULN – 2.5 x ULN	>2.5 x ULN – 5 x ULN	>5 x ULN – 10 x ULN	> 10 x ULN
Haemoglobin (g/dl) increased	> ULN and increase from baseline]0 ;2] (g/dl)	> ULN and increase from baseline]2 ;4] (g/dl)	> ULN and increase from baseline > 4 (g/dl)	-
Haemoglobin (g/dl) - Anemia	[10;LLN[[8;10[< 8	-
White Blood Cells (g/l) - Low	[3.0;LLN[[2.0;3.0[[1.0;2.0[< 1.0

S 64315

CL1-64315-004 – Statistical Analysis Plan – Final V1.0

Parameter	Grade 1	Grade 2	Grade 3	Grade 4
Neutrophils (g/l) - Low	[1.5;LLN[[1.0;1.5[[0.5;1.0[<0.5
Lymphocytes (g/L) - Low	[0.8;LLN[[0.5;0.8[[0.2;0.5[<0.2
Platelets (g/L) - Low	[75;LLN[[50;75[[25;50[<25
aPTT (sec) - High	>ULN – 1.5 x ULN	>1.5 x ULN – 2.5 x ULN	>2.5 x ULN	-
ALT increased (IU/L)	>ULN – 3.0 x ULN if baseline is normal [\leq ULN]; 1.5 x baseline – 3.0 x baseline if baseline is abnormal [> ULN]	>3.0 x ULN – 5.0 x ULN if baseline is normal [\leq ULN]; >3.0 x baseline – 5.0 x baseline if baseline is abnormal [> ULN]	>5.0 x ULN – 20.0 x ULN if baseline is normal [\leq ULN]; >5.0 x baseline – 20.0 x baseline if baseline is abnormal [> ULN]	>20.0 x ULN if baseline is normal [\leq ULN]; >20.0 x baseline if baseline is abnormal [> ULN]
ALP increased (IU/L)	>ULN – 2.5 x ULN if baseline is normal [\leq ULN]; 2.0 x baseline – 2.5 x baseline if baseline is abnormal [> ULN]	>2.5 x ULN – 5.0 x ULN if baseline is normal [\leq ULN]; 2.5 x baseline – 5.0 x baseline if baseline is abnormal [> ULN]	>5.0 x ULN – 20.0 x ULN if baseline is normal [\leq ULN]; >5.0 x baseline – 20.0 x baseline if baseline is abnormal [> ULN]	>20.0 x ULN if baseline is normal [\leq ULN]; >20.0 x baseline if baseline is abnormal [> ULN]

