AST increased (IU/L)	>ULN – 3.0 x ULN if baseline is normal [\leq ULN]; 1.5 x baseline – 3.0 x baseline if baseline is abnormal [> ULN]	>3.0 x ULN – 5.0 x ULN if baseline is normal [\leq ULN]; >3.0 x baseline – 5.0 x baseline if baseline is abnormal [> ULN]	>5.0 x ULN – 20.0 x ULN if baseline is normal [\leq ULN]; >5.0 x baseline – 20.0 x baseline if baseline is abnormal [> ULN]	>20.0 x ULN if baseline is normal [\leq ULN]; >20.0 x baseline if baseline is abnormal [> ULN]
GGT increased (IU/L)	>ULN – 2.5 x ULN if baseline is normal [\leq ULN]; 2.0 x baseline – 2.5 x baseline if baseline is abnormal [> ULN]	>2.5 x ULN – 5.0 x ULN if baseline is normal [\leq ULN]; >2.5 x baseline – 5.0 x baseline if baseline is abnormal [> ULN]	>5.0 x ULN – 20.0 x ULN if baseline is normal [\leq ULN]; >5.0 x baseline – 20.0 x baseline if baseline is abnormal [> ULN]	>20.0 x ULN if baseline is normal [\leq ULN]; >20.0 x baseline if baseline is abnormal [> ULN]

Any grade corresponds to a laboratory value with NCI-CTCAE version 5.0 grade 0, 1, 2, 3 or 4.

A grade 0 corresponds to a laboratory value within limit or reference range.

The LOWEST value for a patient is defined as the lowest absolute laboratory value during the treatment period.

A lowest value for a cycle is defined as the lowest laboratory value in that cycle.

The time to lowest value is defined from the date of the first IMP intake to the sampling date of the lowest value.

The time to lowest value in a cycle is defined from the first date of IMP intake in that cycle to the sampling date of the lowest value.

The HIGHEST value for a patient is defined as the highest laboratory value during the treatment period.

A highest value for a cycle is defined as the highest laboratory value in that cycle.

The time to highest value is defined from the date of the first IMP intake to the sampling date of the highest value.

Urinary results

The category positive includes results '+', '++', '+++', and '++++'.

The category negative corresponds to 'Absent' class.

Creatinine clearance

Creatinine clearance will be approximated by MDRD_GFR. This will be calculate as:

$\text{MDRD_GFR (mL/min/1.73m}^2\text{)} = 175 \times (\text{serum creatinine in mg/dL})^{-1.154} \times \text{age}^{-0.203} \times 0.742$ (if female) $\times 1.212$ (if black race).

Serum creatinine conversion:

$\text{Serum creatinine (mg/mL)} = \text{Serum creatinine (}\mu\text{mol/L)}/88.4$.

MDRD_GFR will be categorised in 4 categories:

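### The SAP's liver laboratory tables grade ALT, AST and bilirubin separately, so they cannot show whether the protocol's combined hepatic criterion was met; one joint table and listing in ULN multiples would close the gap.

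*SAP*

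**What the plan says.** **Laboratory displays.** SAP 3.4.4 promises, for each gradable test, descriptive values and "worst grade on treatment according to the grade at baseline will be provided for gradable parameters". Table (3.4.4) 1 marks ALT, AST and total bilirubin as not gradable at baseline, so the baseline side is covered by the later rule "for parameters gradable post-baseline but non-gradable at baseline, in which case only baseline values will be presented". In effect each of the three gets a baseline description by reference range and, separately, a worst on-treatment grade.

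**Grades.** SAP Table (4.2) 4 uses multiples of ULN if baseline is normal and multiples of baseline otherwise. ALT and AST Grade 1 with a raised baseline is "1.5 x baseline – 3.0 x baseline if baseline is abnormal [> ULN"]. Bilirubin Grade 2 with a normal baseline is ">1.5 x ULN – 3.0 x ULN if baseline is normal".

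**The combined criterion.** The DLT table (protocol 4.1.3.5, repeated in SAP 4.2.3.1) includes "AST or ALT ≥ 3 xULN along with a total bilirubin > 2.0 xULN" with Hy's law confirmed. A variant for raised baselines follows: AST or ALT above both 2.0 x baseline and 3.0xULN, or above 8.0xULN, whichever is lower, with bilirubin above both 2.0 x baseline and 2.0xULN. Protocol Table (8.12) 1 uses nearly the same thresholds for permanent discontinuation, and its footnote c defines a combined elevation as "total bilirubin increase to the defined threshold concurrently with ALT/AST increase to the defined threshold".

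**DLT output.** SAP 4.2.3.1 takes DLTs as the investigator entered them and does not re-derive them. SAP 3.4.1 counts patients with a DLT up to the end of cycle 1 and lists DLTs, both in the DLT-evaluable set (DLTES).

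**The concern.** The criterion needs two facts about one patient at one time: an aminotransferase level and a bilirubin level. A table of worst ALT grade and a table of worst bilirubin grade give neither the pairing nor the timing, since the two maxima may come from different dates or different patients. Grades are also too coarse for the thresholds, and for raised baselines they sit on a different scale from ULN.

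Safety is the only objective this SAP analyses, and liver is one of the risks for which protocol section 8 sets out mitigation. Protocol 2.2.2 names ALT and AST increases among the most frequent investigation terms. If the laboratory section cannot test the protocol's own combined liver criterion, a reader of the report has no independent check on whether every qualifying case was recognised and declared.

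**Working it through.** Everything is in multiples of ULN. The thresholds are the numeric ones only; relatedness and confirmation of Hy's law are clinical judgements and are not modelled.

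**Inputs**
- Entry limit: "AST and ALT < 1.5 x ULN and" (protocol 5.3.2). Protocol 6.1.2 allows up to and including 1.5 before LID1. A baseline b between 1.0 and 1.5 is therefore possible.
- ALT/AST grades, normal baseline: Grade 1 to 3.0, Grade 2 to 5.0. Raised baseline: Grade 1 to 3.0b, Grade 2 to 5.0b (SAP Table (4.2) 4).
- Bilirubin grades, normal baseline: Grade 2 above 1.5 to 3.0, Grade 3 above 3.0 to 10.0.

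**Step 1: normal baselines.** The 2.0 bilirubin cut lies inside Grade 2, so grade cannot separate cases on either side of it.

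| ALT | Bilirubin | Numeric combined thresholds | Displayed |
|---|---|---|---|
| 4.0 | 2.5 | met | ALT Grade 2, bilirubin Grade 2 |
| 4.0 | 1.8 | not met | ALT Grade 2, bilirubin Grade 2 |

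This needs no abnormal baseline. Pairing the two grades within a patient would not help either, because both rows give the same pair.

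**Step 2: raised ALT or AST baseline.** The top of Grade 1 is 3.0 x b:

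| b | Top of Grade 1 = 3.0 x b |
|---|---|
| 1.1 | 3.30 |
| 1.2 | 3.60 |
| 1.4 | 4.20 |
| 1.49 | 4.47 |

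At the entry limit the top of Grade 1 is just under 3.0 x 1.5 = 4.5. Any b above 1.0 therefore allows a value above 3xULN to be Grade 1.

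**Step 3: the raised-baseline criterion in the same range.** For b below 1.5, 2.0 x b is below 3.0, so the requirement of exceeding both limits reduces to ALT or AST above 3.0xULN. Take b = 1.4 with normal baseline bilirubin:
- ALT 4.0 is 4.0/1.4 = 2.86 x baseline, so Grade 1. It exceeds 2.0 x 1.4 = 2.8 and 3.0, so the aminotransferase half is met.
- With bilirubin 2.5 the thresholds are met; with 1.8 they are not. Both cases display as ALT Grade 1, bilirubin Grade 2.

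**Step 4: how narrow the example is.** For ALT 4.0 to be Grade 1, b must be at least 4.0/3.0 = 1.33, against an entry ceiling of 1.5. For bilirubin to be Grade 2 from a normal baseline it must not exceed 3.0. With a normal ALT baseline, a value above 3.0 is always Grade 2 or higher.

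**Step 5: what the other outputs cover.**
- A DLT declared in cycle 1 in a DLTES patient is counted and listed by type, preferred term and verbatim.
- The count stops at the end of cycle 1, although SAP 1.2 defines DLT incidence to the end of each cycle and protocol 10.4.4.2 asks for a table of later DLTs. The listing sentence has no stated cycle limit but is confined to the DLTES.
- A patient who stops before C1D28 for a reason other than a DLT leaves the DLTES (SAP 2.1).
- AE tables by system organ class and preferred term are not specified to show concurrence of two laboratory values.

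**The case against.** The strongest reply is that liver toxicity with consequences will be reported anyway. Protocol 8.2 requires a laboratory abnormality that delays dosing or leads to discontinuation to be recorded as an AE, unless it supports a diagnosis already recorded as one. SAP 3.4.2 tabulates emergent AEs by worst grade, relationship, action taken and outcome, over the treatment period plus 30 days and without a cycle limit. SAP 3.2.1 gives withdrawal reasons for each cycle. This stands. A reader might infer that a liver signal which stopped treatment could vanish from the report; the documents do not support that.

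A second reply is that the SAP does what the protocol asks: 10.4.4.2 specifies CTCAE v5.0 grading and per-test shift tables. This also stands, and a reading of the baseline-relative grades as a mistake would be wrong.

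A third is that leaving DLTs as declared is sound, because a hepatic DLT depends on causality and on confirmation of Hy's law, which thresholds cannot supply. That is right, and it determines how the added display should be labelled.

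Finally, the table shells are in a separate document (SAP 1), so a joint liver table may exist there. The SAP text does not plan one.

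What survives is a check that none of the outputs described in the SAP provides: finding from the laboratory data a qualifying pair that was not declared, that arose after cycle 1, or that arose in a patient outside the DLTES.

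**Conclusion.** The planned liver displays cannot answer whether the combined, concurrent hepatic criterion was met, and this is so even when every baseline is normal. A smaller, additional effect is that with baseline ALT or AST between 1.0 and 1.5xULN, values from just above 3xULN up to 3 x baseline, at most just under 4.5xULN, are shown as Grade 1. The number of patients with such a baseline is not in the documents, so the frequency of this second effect is unknown.

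It is tempting to say that ALT of 4xULN with bilirubin above 2xULN will simply show as Grade 1 and Grade 2. That needs baseline ALT of at least 1.33xULN and bilirubin no higher than 3xULN from a normal baseline; with a normal ALT baseline the ALT would be Grade 2.

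This is a gap measured against the protocol's own DLT definition, not a departure from its analysis section. It is worth closing because it is cheap and safety is the purpose of the report. The conclusion assumes that the separate shells contain no joint liver display.

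**What to change.** Keep the CTCAE tables unchanged. Add to SAP 3.4.4, in the Safety Set, by dose level and overall, for the whole treatment period:

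1. One table giving peak AST or ALT and peak total bilirubin in ULN multiples, and the number of patients whose AST or ALT and bilirubin in the same sample meet the protocol's existing numeric thresholds, with the elevated-baseline variant applied where it belongs.
2. One listing of those patients with baseline values, sampling dates, AST, ALT, bilirubin and ALP in ULN multiples, and whether a DLT or AE was declared. ALP is needed because the normal-baseline rule in protocol Table (8.12) 1 refers to cholestasis.

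Label both as a laboratory screen, not a re-derivation of DLTs. No clinical threshold changes. The SAP already adds threshold classes for QTcF (3.4.6) and LVEF (3.4.7), and SAP 4.2.3.4 says that laboratory reference limits are in the database. The cost is a small amount of extra programming.
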